11.2 Statistical Analyses

Data will be summarized descriptively within each phase overall and by subgroups of interest (e.g. cohort). The descriptive summary including demographics and baseline variables will include counts and percentages for categorical variables and means, medians, standard deviations, and quartiles for continuous variables.

ORR at 6 months, the primary outcome for Phase II, will be summarized using counts and percentages. Logistic regression will be used to compare the ORR between the two cohorts as well as to identify risk factors associated with ORR. Other binary outcomes (e.g. disease control at 6 months (SD+PR+CR) and immunologic response) will be analyzed using the same methods.

Time to event outcomes include overall survival (OS) and progression free survival (PFS). Overall survival is defined as the time from the first dose until death. Individuals without an event will be censored at the date of last contact. Progression free survival is defined as the time from the first dose until progression or death. Individuals who die will be counted as having progressed. Individuals without an event will be censored at the date of the last evaluation for progression. Kaplan-Meier curves will be used to graphically summarize the survival function and to estimate the median time to event and the proportion event-free at key intervals (e.g. 6 months) along with 95% confidence intervals. Cox proportional hazards models will be used to compare Cohorts A and B and to identify risk factors associated with OS and PFS. Graphical techniques (e.g. log-log plots) and formal statistical testing (e.g. Schoenfeld tests) will be used to assess the proportional hazards assumption. If necessary, alternate models (e.g. incorporating a time variable) will be considered.

Safety will be monitored continuously throughout the study, including the phase II component. Weekly team meetings and a minimum of monthly investigator calls will be conducted to review ongoing and resolved toxicity.

Exploratory correlative outcomes are an important part of the study. Paired tumor biopsies will be collected prior to and after initial treatment. Continuous measurements (e.g. density of immune cells, peripheral blood cytokine expression, percentage of CD8+ Tcells expressing ≥ 2 inhibitory receptors, and CD8+ cytokine expression) will be evaluated graphically (e.g. histograms) and numerically (e.g. means, medians) to determine whether or not a transformation (e.g. log) is appropriate. Once the appropriate scale has been determined, graphical techniques, including but not limited to boxplots spaghetti plots, will be used to summarize the values at each time point and the change from pre-to post- treatment. The

means and 95% confidence intervals of each of these quantities will be estimated. A variety of tools including Wilcoxon rank-sum tests and linear regression, with the change as the outcome variable, will be used to determine whether there is a significant change within each group, whether the changes differ between cohorts, and the association between immunologic parameters and response status (CR/PR or SD vs PD). Linear mixed effects models, which account for the correlation between repeated measurements from an individual and allow the inclusion of additional time points, will also be explored. The baseline and change scores will also be considered as potential risk factors for ORR, OS, and PFS using the analysis techniques described above. Serial samples of PBMC and plasma will be evaluated in a similar manner with greater emphasis on the longitudinal modeling due to the greater abundance of repeat measurements.

Genomic sequencing library construction, whole genome/exome sequencing, whole transcriptome sequencing, microbial sequencing, neoepitope prediction, mutation burden, and bioinformatic analysis may be performed either at an on-campus laboratory or at an off-campus sequencing service. All the samples will be de-identified before sending to any laboratory for sequencing. The FASTQ files, BAM files and VCF files will be generated and analyzed. Other sequencing assays may be performed on a subset of samples according to specific requirements of collaboration projects. Genomic sequencing data will be stored and computations conducted using a JH IT managed subscription of Azure.

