1. OBJECTIVES

1.1 Primary Objectives

1. Phase I: To determine the recommended phase II dose (RP2D) of copanlisib with fixed dose nivolumab
2. Phase II/Clinical: To determine 6-month objective response rate (ORR) of patients treated with copanlisib and nivolumab and compare the ORR of patients in Cohort A (MSS colorectal cancer patients with PIK3CA mutations) and Cohort B (MSS colorectal cancer patients with WT PIK3CA)

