1.5 Study Design

This is a multi-center, open-label, Phase I/II study. Phase 1 consists of a 3+3 dose de-escalation design to determine the dose of copanlisib for use in combination with nivolumab. Approximately 6-18 subjects with solid tumors will be treated in Phase I and will be monitored for dose limiting toxicities (DLTs) through their first cycle of treatment. Complete information on the definition of DLTs and dose de-escalation rules can be found in **Section 4.3**.

The Phase II portion of the study will evaluate the safety and clinical activity of copanlisib and nivolumab in two cohorts of patients with previously treated metastatic colon cancer. Cohort A will enroll patients with PI3K mutation and Cohort B will enroll patients with wildtype PI3K status. Twenty-one patients are targeted for enrollment in each cohort, for an approximate total of 42 patients in Phase II. Enrollment in Phase II will be initiated once the recommended phase II dose (RP2D) has been determined in Phase I.

For all patients, the study will consist of a screening period, a treatment period, and a follow-up period. Screening evaluations will be done within 28 days prior to the start of study treatment.

Each treatment cycle is 28 days. Patients in both Phase I and Phase II will receive nivolumab on Day 1 of each cycle (every 4 weeks) and copanlisib on either Day 1, Day 8, and Day 15 of each cycle (3 week on, one week off) or on Day 1 and 15 of each cycle (every 2 weeks), depending on the dose level and RP2D. Complete information on study drug administration, schedule, and dosing can be found in **Section 4.2**.

Phase II enrollment will be carried out in 2 stages so that the study can terminate early if the combination of copanlisib and nivolumab is not sufficiently effective. In the first stage, 12 subjects will be accrued to each cohort. If there are no responders among the first 12 patients, the study will be terminated for futility. Otherwise, 9 additional patients will be accrued for a total of 21 treated subjects. If ≥ 3 out of the 21 patients have a response, then the trial will be considered a success for that cohort.

Clinical and immune responses will be evaluated at baseline and during treatment through tumor assessments, biopsies, and PBMC and plasma collection. Tumor assessments will be made using RECIST 1.1.

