11. STATISTICAL CONSIDERATIONS

11.1 Sample Size

Phase I will be enrolled in a standard 3+3 design with up to 18 patients. For the purposes of dose finding, DLTs will be evaluated during the first cycle for each patient. An initial cohort of 3 patients will be enrolled. If 0-1/3 have a DLT then 3 additional patients will be enrolled at the same dose level. If 2-3/3 DLTs are observed, then the dose will be considered too toxic and the next lower dose level will be enrolled. The RP2D is the dose at which $\leq 1/6$ patients have a DLT (i.e. if 0/3 of the initial patients have a DLT then an additional 3 will be recruited at the highest feasible dose to establish the RP2D).

During Phase II 42 patients will be recruited: 21 patients with colorectal cancer with PIK3CA mutation (cohort A) and 21 with WT PIK3CA with known lack of sensitivity to immune checkpoint inhibitor therapy (cohort B). ORR (CR+PR) at 6 months the primary endpoint and will be evaluated separately in each cohort. Enrollment will be carried out in 2 stages so that the study can terminate early if the combination of copanlisib and nivolumab is not sufficiently effective. A design similar to Simon's minimax design with relaxed futility stopping will be employed to test the null hypothesis that the true ORR is 5% or less.³⁰⁻³¹ In the first stage, 12 subjects will be accrued in each cohort. If there are no responders among the first 12 patients, the study will be terminated for futility. Otherwise, 9 additional patients will be accrued for a

total of 21 treated subjects. Patients who withdraw consent before disease re-evaluation will not be considered evaluable for response and may be replaced. Patients who come off of study prior to disease re-evaluation with imaging due to clinical deterioration will be considered evaluable for response and will be coded as progressing. If ≥ 3 out of the 21 patients have a response, then the trial will be considered a success for that cohort. If the true response rate is 20% (alternative hypothesis rate), then the probability of a declaring the treatment a success is 0.80 (power). If the true response rate is 5% (null hypothesis rate), then the probability of declaring the treatment a success is 0.08 (type I error).

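### Logistic regression is the only method named for comparing ORR between Cohorts A and B, yet the 0/12 futility stop often leaves it with no finite odds ratio and no designated test

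*Combined protocol and SAP*

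**What the plan says.** Section 1.1 makes the comparison part of the Phase II primary objective: to determine 6-month ORR and to "compare the ORR of patients in Cohort A" with that in Cohort B. Section 11.2 gives the method: "Logistic regression will be used to compare the ORR between the two cohorts". The same model is used to look for factors associated with ORR, and the same methods apply to other binary outcomes such as disease control. Apart from that, "ORR at 6 months, the primary outcome for Phase II, will be summarized using counts and percentages".

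Section 11.2 does not say whether inference is by Wald, score or likelihood-ratio test, and it names no exact or penalised method and no interval for ORR. Its one allowance for alternative models belongs to the Cox analysis. The rank-sum and linear-regression tools are for changes in continuous correlative measures.

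Section 11.1 sets the stopping rule: "In the first stage, 12 subjects will be accrued in each cohort", and "If there are no responders among the first 12 patients, the study will be terminated for futility". Otherwise 9 more patients are added, for 21. ORR "will be evaluated separately in each cohort". With at least 3 responses in 21, Section 1.5 says, "then the trial will be considered a success for that cohort".

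**The concern.** A logistic model with cohort as its covariate estimates an odds ratio from a 2x2 table. If one cohort has no responders, the likelihood keeps rising as the log odds ratio moves to plus or minus infinity, so there is no finite estimate. The futility rule produces exactly this table.

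At stake is a comparison named in the primary objective. It could end with no finite estimate and no two-sided interval, and with a p-value that depends on which of the model's tests is chosen after the counts are known.

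**Working it through.** **Inputs (Section 11.1).** Stage 1 n = 12 per cohort; stop at 0/12; otherwise n = 21; success at 3 or more responses; null ORR 5%, alternative 20%. Assumptions: the cohorts are independent, and the two rates are crossed, because the plan states no joint scenario.

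**Reproducing the plan's figures.** P(success) = sum over x = 1 to 12 of P(X1 = x) × P(X2 ≥ 3 − x), with X1 ~ Bin(12, p) and X2 ~ Bin(9, p). This gives 0.0804 at 5% (stated 0.08) and 0.8033 at 20% (stated 0.80). Both agree.

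**How often a cohort has no responders.** Let q = (1 − p)^12 be the chance of 0/12: 0.95^12 = 0.540 and 0.80^12 = 0.0687. Let z = (1 − p)^21: 0.3406 and 0.0092. Section 11.1 speaks of terminating the study, so three readings were checked.

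| True ORR A/B | Stop per cohort, or either cohort ends the study: 1 − (1 − qA)(1 − qB) | Stop only if both at 0/12: qA·qB + zA(1 − qB) + zB(1 − qA) | Both at 0/12: qA·qB |
|---|---|---|---|
| 5%/5% | 0.789 | 0.605 | 0.292 |
| 20%/5% | 0.572 | 0.359 | 0.037 |
| 20%/20% | 0.133 | 0.022 | 0.005 |

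**What the model gives for 4/21 vs 0/12.**
- Maximum likelihood: the log odds ratio is 10.1, 20.1 and 25.1 after 10, 20 and 25 iterations, with standard errors of about 57, 8,440 and 103,000. It diverges, and the Wald p-value goes to 1.
- Likelihood ratio: 2 × [−10.225 − (−12.188)] = 3.93, p = 0.048. The profile lower limit for the odds ratio is 1.03, with no finite upper limit.
- Score: (4/21) / √[(4/33)(29/33)(1/21 + 1/12)] = 0.1905/0.1181 = 1.61, p = 0.107.
- Fisher, for reference: (5985 + 4620 + 495)/40920 = 0.271.

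With both cohorts at zero the response does not vary, and nothing is estimable from the model.

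**How often score and likelihood ratio disagree at 0.05 because of a zero cohort.** For x/21 vs 0/12, likelihood ratio is significant from x = 4 and score from x = 6, so they disagree at x = 4 and 5. Under the two-stage rule, P(4 or 5 responses in 21) is 0.3933 at 20% and 0.0181 at 5%.
- 20%/5%: 0.540 × 0.3933 + 0.0687 × 0.0181 = 0.214.
- 20%/20%: 2 × 0.0687 × 0.3933 = 0.054.

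If either cohort at 0/12 ends the study at 12 vs 12, the only disagreement is 3/12 vs 0/12. P(3/12) is 0.2362 at 20% and 0.0173 at 5%.
- 20%/5%: 0.540 × 0.2362 + 0.0687 × 0.0173 = 0.129.
- 20%/20%: 2 × 0.0687 × 0.2362 = 0.032.

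**Error rates by exact enumeration, per-cohort stopping.** At 20%/20% the false-positive rates are 11.4% for likelihood ratio (8.6 points from zero-cohort tables), 6.0% for score and 2.5% for Fisher. Over common ORRs up to 70%, Fisher peaks at 3.2%, near 26%. Its power at 20% vs 5% is 8.5%.

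**Interval for the ORR difference, 4/21 vs 0/12.** The difference is 4/21 − 0 = 19 points. Inverting two one-sided exact unconditional score tests at 2.5% gives about −8.9 to +41.9 points. The exact binomial upper limit for 0/12 is 1 − 0.025^(1/12) = 26.5%.

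**The case against.** The plan says logistic regression, not Wald. A reader might infer that a zero cohort leaves nothing to report, and the documents do not support that. With only one cohort at zero, the same model still gives a likelihood-ratio or score p-value and a one-sided profile limit, and the counts and percentages are reported in every case. What is missing is a finite odds ratio, a two-sided interval and a chosen test. Only with both cohorts at zero does the model give nothing.

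A reader might also count Wald as a third competing test, which raises the disagreement to 34% (20%/5%) and 8.6% (20%/20%). That treats a degenerate result as a real non-significant one. The fair figures are those for score against likelihood ratio.

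The futility wording is ambiguous, and the error rates above assume per-cohort stopping. This stands as a limit on those figures. It does not remove the zero-cohort problem, which remains under all three readings.

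Finally, Section 11.1 gives no power, alpha or success rule for A vs B, and the proposed test will seldom reach significance. This lowers the urgency. It does not excuse leaving the analysis of a primary-objective comparison undefined for an outcome that the design creates.

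**Conclusion.** The concern holds as a gap in Section 11.2 that should be fixed. Under the crossed 5% and 20% rates, the named method has no finite odds ratio in 79%, 57% and 13% of trials, or 61%, 36% and 2.2% under the most favourable reading of the stop. When only one cohort is at zero, two usable tests from the same model remain. At 20%/5% they give opposite answers at 0.05 because of a zero cohort in 21.4% of trials with per-cohort stopping, or 12.9% if either cohort at 0/12 ends the study. At 20%/20% the figures are 5.4% and 3.2%. Falling back on the likelihood-ratio test would carry an 11.4% false-positive rate at 20%/20%. At 5%/5% nearly all results are non-significant by any test (likelihood ratio rejects in 2.0%), so the loss there is the estimate and interval.

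A reader might go further and doubt the Phase II success declarations. The documents do not support that: the stop and success rules use responder counts within each cohort, and their stated error rates reproduce.

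**What to change.** Amend Section 11.2 before responses are compared between cohorts:

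1. Use the two-sided Fisher exact test as the p-value for the cohort comparison of ORR.
2. Report the ORR difference with an exact unconditional 95% interval from two one-sided score tests at 2.5% each.
3. If both cohorts have zero responders, report each cohort's exact binomial interval (0/12: 0 to 26.5%) and do no test.
4. Use Firth-penalised logistic regression where the same model serves ORR risk factors or other binary outcomes and a zero cell occurs.
5. Describe the comparison as mainly estimation.

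The cost is SAP wording only, with no new data and no change to the stop or success rules. The drawbacks are that Fisher is conservative, so a true difference of 20% vs 5% will usually be missed, and that the interval is wide. The 3.2% error ceiling and 8.5% power are for per-cohort stopping and should be recomputed if a study-level stop is intended.

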11.3 Safety Analyses

AE data will be listed individually and incidence of AEs will be summarized by system organ class and preferred terms within a system organ class for Phase I and Phase II (overall and within each cohort). When calculating the incidence of AEs, each AE will be counted only once for a given subject. In analyses of grade and causality, if the same AE occurs on multiple occasions, the highest grade and strongest relationship to study drug will be assumed. If 2 or more AEs are reported as a unit, the individual terms will be reported as separate experiences. Incidence, measured as time to first AE, will be analyzed for all AEs and by type using the methods described above. In addition, the event rates (which incorporate multiple AEs of the same type) will be analyzed using Negative Binomial regression.

Changes in vital signs, hematology and clinical chemistry parameters from baseline to the end of the study will be examined. Toxicity will be tabulated by type and grade. Toxicities will be characterized according to the CTCAE version 5.0. Treatment-emergent changes from normal to abnormal values in key laboratory parameters will be identified. Incidence and rate evaluations will follow the methods described for AEs.

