5.6 Reporting

5.6.1 General

[figure not shown]
All adverse events (both expected and unexpected) will be captured on the appropriate study-specific case report forms (CRFs).

Adverse events experienced by subjects will be collected and reported from the first dose of the study drug, throughout the study, and will only be followed for 30 days (or within 7 days prior to initiation of a new anti-cancer treatment, whichever comes first) unless related to the study drug(s). Adverse events related to the study drug(s) will be monitored for resolution of toxicity to \leq grade 1, stabilization, or determined to be irreversible by the investigator.

SAEs that occur following the subject’s written consent to participate in the study through 100 days (+ 14 day reporting window) after the last infusion of study drug (or within 7 days prior to initiation of a new anti-cancer treatment, whichever comes first) will be collected and reported.

All SAEs, regardless of causality to study drug, must be reported within 24 hours of initial notification of the SAE to the IND Sponsor, BMS, and Bayer using the SAE Reporting Form found in **Appendix F**. If this falls on a weekend or holiday, an email notification is acceptable but must be followed by an SAE reporting form on the next business day.

SAE reports and any other relevant safety information are to be sent to:

After the initial SAE report, the investigator is required to proactively follow each subject and provide further information to the safety department in regards to the subject's condition.

All SAE(s) will be followed until:

- Resolution
- The condition stabilizes
- The event is otherwise explained
- The subject is lost to follow-up
- Death

As soon as relevant information is available, a follow-up SAE report will be submitted to the IND Sponsor, BMS, and Bayer.

The Sponsor will reconcile the clinical database SAE cases (case level only) transmitted to BMS Global Pharmacovigilance [REDACTED].

- The Investigator will request from BMS GPV&E [REDACTED] the SAE reconciliation report and include the BMS protocol number every 3 months and prior to data base lock or final data summary.
- GPV&E will send the investigator the report to verify and confirm all SAEs have been transmitted to BMS GPV&E.

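### Time to first AE is sent to the Kaplan-Meier and Cox methods for OS and PFS, whose event and censoring rules do not fit AEs; a cumulative incidence estimate with death competing is needed

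*Combined protocol and SAP*

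**What the plan says.** Section 11.3 plans three AE summaries. The first is crude per-subject incidence by system organ class and preferred term. The second is time to first AE: "Incidence, measured as time to first AE, will be analyzed for all AEs and by type using the methods described above". The third is event rates by Negative Binomial regression. The same section applies the AE methods for incidence and rates to the laboratory and toxicity evaluations, so the point extends to those.

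The time-to-event methods above are in section 11.2. The estimator is Kaplan-Meier: "Kaplan-Meier curves will be used to graphically summarize the survival function and to estimate the median time to event". Cox models compare the cohorts. Two sets of event and censoring rules are given:

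- OS: "Overall survival is defined as the time from the first dose until death", and "Individuals without an event will be censored at the date of last contact".
- PFS: "Individuals who die will be counted as having progressed", and "Individuals without an event will be censored at the date of the last evaluation for progression".

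Neither section states the event, risk window, censoring date or competing events for time to first AE.

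AE collection has its own limits. Under section 5.6.1, AEs "will only be followed for 30 days" or until shortly before a new anti-cancer treatment, with drug-related AEs followed longer. SAEs are collected for 100 days plus a 14-day reporting window, or until shortly before new treatment. Survival contact continues much longer: up to 2 years in the study calendars (section 8, footnote 22) and up to 3 years in section 4.7.

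**The concern.** Death before the AE makes the AE impossible, so it is a competing event. If such deaths are treated as censored, 1-KM estimates the AE risk in a hypothetical population in which nobody dies first, not the share of patients who have the AE. Deaths are unlikely to be rare here: section 3.1 admits patients with metastatic or unresectable disease, at least two prior lines in the colorectal cohorts, and a life-expectancy criterion of 3 months.

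The borrowed censoring dates add a second difficulty. They were written for outcomes that are observed until last contact or last scan, whereas AE collection usually stops earlier than survival contact.

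At stake are the reported time-to-first-AE curves and percentages, overall and by type. They bear on the secondary objective of characterising the toxicity of the combination (section 1.2). Two analysts following the text could publish materially different figures from the same data.

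**Working it through.** The plan gives no AE-incidence, death or discontinuation figure for this analysis, so there is nothing to reproduce. The check has two parts.

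**1. Each borrowed rule applied to time to first AE**

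- *OS rule, censoring at last contact.* For a patient who dies without the AE, last contact is death, so death becomes a censoring and 1-KM is pushed up. A survivor whose AE collection has ended stays in the risk set through survival follow-up although no new AE would be recorded, so 1-KM is pushed down.
- *PFS rule.* Death counts as an event, so the curve describes AE or death, not AE incidence.
- *Censoring at end of AE collection* (a common choice, not stated in the plan). The downward push goes, but deaths without the AE are still censored, so 1-KM overstates.

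**2. Size under assumed hazards**

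Assumed inputs, none from the documents: constant, independent hazards; horizon T = 6 months; 1-KM with death and end of collection censored (p) of 20% or 40%; median time to death 6, 12 or 24 months; median time to end of AE collection 3, 4 or 6 months. The cohort size of 21 is from section 1.5.

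Hazards per month:

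- AE: a = -ln(1-p)/6, which is 0.0372 for 20% and 0.0851 for 40%.
- Death: d = ln2/median, which is 0.1155, 0.0578 or 0.0289.
- End of collection: e = ln2/median, which is 0.2310, 0.1733 or 0.1155.

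Formulas:

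- Cumulative incidence, death competing and end of collection censored: a/(a+d) × [1-exp(-(a+d)T)].
- 1-KM under the literal last-contact rule: a/(a+e) × [1-exp(-(a+e)T)]. The death hazard cancels because it is taken as equal before and after collection ends, and no AE is recorded after that.
- PFS rule, AE or death: 1-(1-p) × exp(-dT).

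Example for p = 20% and median death 12 months: 0.0372/0.0950 × [1-exp(-0.570)] = 17.0%.

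| Quantity at 6 months | p = 20% | p = 40% |
|---|---|---|
| 1-KM, censoring death and end of collection | 20% | 40% |
| Cumulative incidence, death competing (median death 6, 12, 24) | 14.6, 17.0, 18.4% | 29.7, 34.3, 37.0% |
| 1-KM, literal last-contact rule (median end of collection 3, 4, 6) | 11.1, 12.7, 14.6% | 22.9, 26.0, 29.7% |
| 1-KM, PFS rule (median death 6, 12, 24) | 60.0, 43.4, 32.7% | 70.0, 57.6, 49.5% |

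The first row exceeds the second by 1.6 to 5.4 points for 20% (× 21 = about 0.3 to 1.1 patients per cohort), and by 3.0 to 10.3 points for 40% (about 0.6 to 2.2 patients). A simulation with n = 21, p = 20%, median death 12 months and median end of collection 4 months gave 19.7% for 1-KM and 16.8% for Aalen-Johansen, in agreement.

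The second and third formulas have the same form, with e in place of d. In this model the literal last-contact rule therefore understates incidence if patients leave AE collection faster than they die, and overstates it if they leave more slowly. The net direction is not fixed by the text.

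*Early AEs.* If the whole 20% risk falls in month 1, a = -ln(0.8) = 0.2231 with T = 1. The cumulative incidence is then 18.9% (median death 6 months) to 19.7% (24 months), a gap of 0.3 to 1.1 points.

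**The case against.** A reader might infer that the plan itself censors death and end of AE collection, so that AE incidence is overstated, and by a lot. The documents do not support that. In section 11.2 death is the OS event and counts as a PFS event, and neither stated censoring date is the end of AE collection. The upward bias is what follows when last-contact censoring is carried over to AEs, and the same rule also produces a downward one.

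Nor is end of collection a competing event by default. A patient can still have an AE after observation stops, so this is ordinary, possibly informative, censoring. It competes only if the declared target is risk within the collection window. On that target, an assumed AE hazard of 0.05 per month and a competing hazard of 0.1 to 0.3 give a 6-month 1-KM of 25.9% against 19.8% to 12.5%. That larger gap rests on the choice of target as well as on assumed hazards. It would also be wrong to say that all collection ends at 30 days: section 5.6.1 follows drug-related AEs longer and collects SAEs to 100 days. Nothing in the documents shows that the bias differs between cohorts.

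Three further objections stand and limit the point. Crude incidence and Negative Binomial rates are also planned, so the time-to-first-AE estimate is not the only safety summary. Cox models that censor at death are valid comparisons of cause-specific hazards. No DLT, stopping or primary-endpoint rule uses this estimate. What the objections do not supply is a correct estimator for absolute AE risk over time; the crude table does not repair a biased curve printed beside it.

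**Conclusion.** The point holds in limited form. Section 11.3 borrows Kaplan-Meier and Cox methods with no competing-risk estimator, and with OS and PFS rules that do not fit AEs. Censoring deaths without the AE overstates incidence, keeping survivors at risk after collection has ended understates it, and the PFS rule measures something else.

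With death alone competing, 20% by 1-KM corresponds to about 14.6-18.4%, and 40% to about 29.7-37.0%. These ranges rest wholly on assumed constant, independent hazards; early AEs make the gap smaller. The consequence is confined to the reported time-to-first-AE curves and percentages. The change is worth making because those figures serve a stated secondary objective and the better method costs almost nothing.

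**What to change.** In section 11.3, define time to first AE separately from OS and PFS:

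- Estimate incidence, overall and by type and for laboratory toxicities, by the Aalen-Johansen cumulative incidence function, with death without a prior AE as a competing event.
- Censor at the end of the applicable AE collection window (30 days after the last dose or new therapy, with the longer window for SAEs), not at last contact. State how drug-related AEs followed beyond 30 days are handled.
- Treat end of collection as competing only if on-treatment risk is declared as the target.
- Keep cause-specific Cox models for cohort comparisons, and the crude incidence and Negative Binomial rates already planned.

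The cost is a short SAP edit and slightly more analysis work with standard software. No new data are needed, and sample size, primary endpoint, DLT rules and toxicity stopping rule do not change.
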